2.2.1 Protocol deviations

The number and percentage of patients with a critical or major protocol deviation will be summarized by deviation and overall within treatment group, and according to COVID-19 impact (ie, deviations related to the COVID-19 pandemic and deviations not related to the COVID-19 pandemic). Specific deviations related to randomization may be summarized separately. A listing of patients with at least one critical or major deviation will be provided.

2.3 ANALYSIS POPULATIONS

Patients treated without being randomized will not be considered randomized and will not be included in any efficacy population.

The randomized population includes any patient who has been allocated to a randomized treatment regardless of whether the treatment kit was used.

For any patient randomized more than once, only the data associated with the first randomization will be used in any analysis population. The safety experience associated with any later randomization will be assessed separately.

If >10% participants are impacted by the COVID-19 pandemic, additional summaries by COVID-19 subgroups will be provided. Participants impacted by the COVID-19 pandemic are defined as randomized participants with any critical or major deviation related to the COVID-19 pandemic or who permanently discontinued study intervention or study due to the COVID-19 pandemic or a COVID-19 related AE.

2.3.1 Efficacy populations

The primary efficacy analysis population will be the ITT population as defined in [Section 2.3.1.1](#).

2.3.1.1 Intent-to-treat population

The intent-to-treat (ITT) population is the randomized population analyzed according to the treatment group allocated by randomization.

Patients will be analyzed in the treatment group to which they are randomized.

2.3.2 Safety population

The safety population is defined as: All patients who actually received at least 1 dose or partial of a dose of the IMP, analyzed according to the treatment patients actually received.

In addition:

- Nonrandomized but treated patients will be part of the safety population
- Randomized patients for whom it is unclear whether they took the IMP will be included in the safety population as randomized
- For patients on placebo but accidentally exposed to dupilumab, the treatment group allocation for as-treated analysis will be dupilumab group
- For patients on dupilumab but accidentally receive placebo, the actual treatment group allocation for as-treated analysis will be dupilumab group

2.3.3 Pharmacokinetics (PK) population

The PK population will consist of all patients in the safety population with at least one evaluable functional dupilumab concentration result. Patients will be analyzed according to the treatment actually received.

2.3.4 Anti-drug antibody population

The anti-drug antibody (ADA) population will consist of all patients in the safety population with at least one reportable ADA results (either 'ADA negative' or 'ADA positive') after first dose of the study treatment. Patients will be analyzed according to the treatment actually received.

2.4 STATISTICAL METHODS

2.4.1 Demographics and baseline characteristics

Continuous data will be summarized using the number of available data, mean, standard deviation (SD), median, minimum, and maximum for each treatment group. Categorical and ordinal data will be summarized using the number and percentage of patients in each treatment group.

Parameters will be summarized on the randomized population analyzed in the treatment group to which they were randomized. Analyses for the safety population will be included in the appendices if the size of the safety population is different (>10%) from the size of that in the primary analysis population for any treatment group.

Parameters described in [Section 2.1.1](#) will be summarized by treatment group and overall treatment groups using descriptive statistics.

Medical and surgical history will be summarized by treatment group and by system organ class (SOC) and preferred term (PT) sorted by internationally agreed order of SOC and by the

decreasing frequency of PT within SOC based on the overall incidence across treatment groups. Atopic medical history will be summarized separately.

No statistical testing on demographic and baseline characteristic data will be performed.

No specific description of the safety parameters will be provided at baseline. If relevant, the baseline values will be described along with each safety analysis.

2.4.2 Prior or concomitant medications

The prior and concomitant medications will be presented for the randomized population.

Medications will be summarized by treatment group according to the WHO-DD dictionary, considering the first digit of the anatomic category (ATC) class (anatomic category) and the first 3 digits of the ATC class (therapeutic category). All ATC codes corresponding to a medication will be summarized, and patients will be counted once in each ATC category (anatomic or therapeutic) linked to the medication. Therefore patients may be counted several times for the same medication.

The table for prior medications will be sorted by decreasing frequency of ATC followed by all other therapeutic classes based on the overall incidence across treatment groups. In case of equal frequency regarding ATCs (anatomic or therapeutic categories), alphabetical order will be used.

Concomitant medication received during first IMP to last IMP +14 days and concomitant medication received during first IMP to last IMP +98 days will be summarized separately. The tables for concomitant medications will be sorted by decreasing frequency of ATC followed by all other therapeutic classes based on the incidence in the dupilumab 300 q2w group. In case of equal frequency regarding ATCs (anatomic or therapeutic categories), alphabetical order will be used.

Medications will also be summarized by generic name sorted by decreasing frequency based on the incidence in the dupilumab group.

In addition, inhaled corticosteroid in combination with other controllers and reliever medications will be summarized separately.

2.4.2.1 ICS in combination with other controllers

ICS and other COPD controller medications will be identified as the medications reported on the “Prescribed COPD Controller Medications” eCRF page.

Prior COPD controller medications will be summarized by treatment group sorted by decreasing frequency of standard medication name on the incidence in the overall treatment group.

Concomitant COPD controller medications will be summarized by treatment group sorted by decreasing frequency of standard medication name on the incidence in the dupilumab group.

The total daily dose of ICS in COPD controller medication at randomization will be classified as high dose or lower dose according to Appendix G. If a patient takes more than one medication

containing ICS, the ICS dose of different products will be standardized according to equivalent dose specified in [Table 3](#) and [Table 4](#). After conversion, the total daily dose for inhaled corticosteroid will be calculated and classified as high dose or lower dose.

Table 3 - Equivalent dose for inhaled corticosteroids for adults

Inhaled corticosteroid	Equivalent dose (mcg) to 500 mcg Fluticasone propionate (DPI or HFA)
FLUTICASONE FUROATE	200-*
BECLOMETASONE DIPROPIONATE (CFC)	1000
BECLOMETASONE DIPROPIONATE (HFA)	400
BUDESONIDE (DPI)	800
CICLESONIDE (HFA)	320
MOMETASONE FUROATE	440
TRIAMCINOLONE ACETONIDE	2000

ADAPTED FROM GINA 2016 GUIDELINES

HFA=hydrofluoroalkane, DPI= Dry Powder Inhaler

* Fluticasone furoate (FF) dose \geq 200 mcg is converted to equivalent fluticasone propionate (DPI or HFA) dose of (FF dose +1) \times 2.5; FF dose $<$ 200 mcg is converted to equivalent fluticasone propionate (DPI or HFA) dose of FF dose \times 2.5.

Example: A patient received 400 mcg budesonide (DPI) and 440 mcg mometasone furoate. They are equivalent to 250 mcg and 500 mcg fluticasone propionate correspondingly. The combined total daily dose is equivalent to 750 mcg fluticasone propionate and classified as high dose.

Table 4 - Equivalent dose of inhaled corticosteroid for adults (Japan)

Inhaled corticosteroid	Equivalent dose (mcg) to 400 Fluticasone propionate (DPI or HFA)
FLUTICASONE FUROATE	100
BECLOMETHASONE DIPROPIONATE -HFA	400
CICLESONIDE -HFA	400
BUDESONIDE-DPI	800
BUDESONIDE INHALATION SUSPENSION	1.0 mg
BUDESONIDE INHALATION SOLUTION	1000
MOMETASONE FUROATE-DPI	400

Adapted from Japanese Guideline for Adult Asthma 2014

Example: A patient received 400 mcg Beclomethasone dipropionate -HFA and 400 mcg Ciclesonide-HFA. They are both equivalent to 400 fluticasone propionate. The combined total daily dose is equivalent to 800 fluticasone propionate.

Number and percentage of patients on ICS, ICS/LABA, LABA, LAMA, LTRA, Anti-Leukotriene, Methylxanthine and other controller medications at baseline will also be summarized.

2.4.2.1.1 *Compliance*

During the study, the daily intake of each prescribed COPD controller medication will be recorded on the electronic diary every evening. Compliance for the controller medications with ICS component and overall compliance to all prescribed controller medications will be calculated for each patient. For each day, a patient is considered as compliant with the prescribed controller medication with ICS component if the actual dose of each controller medication with ICS component is same as or greater than the prescribed dose. Similarly, a patient is considered as compliant with all controller medication if the actual dose of each controller medication is same as or greater than the prescribed dose.

Compliance for controller medication(s) with ICS component is defined as the number of days when the patient is compliant with the prescribed controller medication(s) with ICS component divided by the number of days the patient stays in the treatment period (from first dose to last dose + 14 days).

Overall controller medication(s) compliance is defined as the number of days when the patient is compliant with all prescribed controller medication divided by the number of days the patient stays in the treatment period.

2.4.3 Extent of investigational medicinal product exposure and compliance

The extent of IMP exposure and compliance will be assessed and summarized by actual treatment within the safety population (Section 2.3.2).

2.4.3.1 *Extent of investigational medicinal product exposure*

The extent of IMP exposure will be assessed by the duration of IMP exposure.

Duration of IMP exposure is defined as last dose date – first dose date + 14 days, regardless of unplanned intermittent discontinuations (see Section 2.5.3 for calculation in case of missing or incomplete data). Duration of IMP exposure will be summarized descriptively as a quantitative variable (number, mean, SD, median, minimum, and maximum). In addition, duration of treatment exposure will also be summarized categorically by numbers and percentages for each of the following categories and cumulatively according to these categories:

- >0 and \leq 2 weeks
- >2 and \leq 4 weeks
- >4 and \leq 8 weeks
- >8 and \leq 12 weeks
- >12 and \leq 16 weeks
- ...
- ...
- >48 and \leq 52 weeks
- >52 weeks and \leq 52 weeks + 3 days
- >52 weeks + 3 days

Additionally, the cumulative duration of treatment exposure will be provided, defined as the sum of the duration of treatment exposure for all patients, and will be expressed in patient years.

2.4.3.2 Compliance

A given administration will be considered noncompliant if the patient did not take the planned dose of treatment as required by the protocol. No imputation will be made for patients with missing or incomplete data.

Percentage of compliance for a patient will be defined as the number of administrations that the patient was compliant divided by the total number of administrations that the patient was planned to take during the treatment epoch defined in [Section 2.1.3.2.2.1](#).

Treatment compliance percentages will be summarized descriptively as quantitative variables (number, mean, SD, median, minimum, and maximum). The percentage of patients whose compliance is <80% will be summarized in [Section 2.4.4.5](#).

Cases of overdose (defined as at least twice the intended dose during an interval of less than 11 days) will be specified in the overdose form and symptoms, if any, entered on separate adverse event forms.

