- a Randomization/baseline visit is defined as Day 1. The visit schedule should be adhered to within ±1 week for the 4-week screening period, ±3 days for the randomized IMP treatment period and ±5 days for the post IMP treatment period. If more than 12 weeks since last on-site scheduled visit, then unscheduled visit is required within 3 weeks of missed scheduled visit (eg, if missed scheduled visit at Week 24, then unscheduled visit must be performed by Week 27; If missed scheduled visit at Week 36, then unscheduled must be performed by Week 39). All the assessments of the missed scheduled on-site visit will need to be carried out at the unscheduled visit.
- b All assessments at Visit 2 (Day 1) are to be conducted pre-IMP dose with the exception of the assessment of local tolerability of SC injections.
- c End-of-treatment visit: See Section 7.1.1 for patients who discontinue treatment prematurely.
- d ECG to be centrally collected & read.
- Chest X-ray to be performed unless a <6-month-old chest x-ray/chest CT/chest MR is available. In case chest-X-ray is not feasible due to local regulations, magnetic resonance imaging (MRI) will be performed.
- f IMP (Dupilumab or placebo) is to be administered every 2 weeks by patient, caregiver or healthcare professional at the patient's home or in a health care facility. Last dose will be given at Week 50. If the patient or Investigator decides not to administer IMP at home, the IMP injections can be performed at the site by way of unscheduled visits. The IMP can be administered at home after training and at least 1 IMP injection at the site and supervised by the Investigator. Patients will be monitored at the study site for a minimum of 30 minutes after injections. See Section 6.1.1 for details. If the patient is unable or unwilling to administer IMP at home, injections can be performed at the site; or arrangements can be made for qualified site personnel and/or health care professionals (eg, visiting nurse service) to administer IMP for the doses that are not scheduled to be given at the study site.

Amended Clinical Trial Protocol 03 EFC15805 - dupilumab

28-Oct-2023 Version number: 1

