6.1.1 Investigational Medicinal Product(s)

The investigational medicinal product (IMP) is administered every 14 ± 3 days (q2w) during the 52-week treatment period (Table 2).

Investigational medicinal product (IMP) will be administered by the Investigator/health care professional or designee following clinic procedures and blood collection. Patients should be monitored for at least 30 minutes after administration of all IMP injections. The monitoring period may be extended as per country specific or local site-specific requirements.

Subcutaneous injection sites should alternate between the upper thighs, 4 quadrants of the abdomen or the upper arms, so that the same site is not injected twice during consecutive administrations.

The first IMP administration will be done by the Investigator or delegate. The patients are allowed to self-inject IMP at home after at least 1 injection at investigational site, supervised by the Investigator or delegate. To train patients how to prepare and inject IMP the Investigator will

28-Oct-2023 Version number: 1

first train the patient at the on-site visit during the treatment period. At this visit the patient will perform the injection under the supervision of the Investigator or delegate. This training must be documented in the patient's study file. Patient injection should only be performed in the abdomen or upper thighs. Patient should also be instructed to monitor for any reaction for at least 30 minutes (or longer per country specific or local site-specific requirements) following injection.

If the patient cannot take all the allocated IMP kits at home (eg. due to a storage issue), the DTP (Direct to Patient) service can be used or the patient may come to the site to pick-up the IMP kits. For doses not given at the study site, diaries will be provided to record information related to the injections. The diary will be kept as source data in the patient's study file.

If the patient is unable or unwilling to administer IMP at home, injections can be performed at the site; or arrangements can be made for qualified site personnel and/or health care professionals (eg, visiting nurse service) to administer IMP for the doses that are not scheduled to be given at the study site.

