7.1.1 Permanent discontinuation

In rare instances, it may be necessary for a patient to permanently discontinue study intervention. If study intervention is permanently discontinued, the participant remains in the study to be evaluated for as per Section 1.3.2 (see the SOA for data to be collected at the time of discontinuation of study intervention).

Permanent intervention discontinuation is any intervention discontinuation associated with the definitive decision from the Investigator not to re-expose the patient to the IMP at any time during the study, or from the patient not to be re-exposed to the IMP whatever the reason.

List of criteria for permanent discontinuation of study intervention

All efforts should be made to document the reason(s) for discontinuation of study intervention and this should be documented in the eCRF.

Patients must be withdrawn from the study intervention for the following reasons:

- At their own request or at the request of their legally authorized representative (legally authorized representative means an individual or judicial or other body authorized under applicable law to consent on behalf of a prospective patient to the patient's participation in the procedure(s) involved in the research).
- If, in the Investigator's opinion, continuation on the study intervention would be detrimental to the patient's well-being.
- At the specific request of the Sponsor.
- In the event of a protocol deviation, at the discretion of the Investigator or the Sponsor.
- Any code broken requested by the Investigator will lead to permanent discontinuation of study intervention.
- Pregnancy.

- Anaphylactic reactions or systemic allergic reactions that are related to IMP and require treatment.
- Diagnosis of a malignancy during study, excluding carcinoma in situ of the cervix, or squamous or basal cell carcinoma of the skin.
- Any opportunistic infection, such as TB or other infections whose nature or course may suggest an immunocompromised status (see Section 10.16, Appendix 16).
- Serum ALT >3 ULN and Total Bilirubin >2ULN (see Section 10.6, Appendix 6).
- Serum ALT >5 ULN if baseline ALT ≤2 ULN or ALT >8 ULN if baseline ALT >2 ULN (see Section 10.6, Appendix 6).
- If the patient misses more than 3 consecutive doses, the patient will be permanently discontinued from the study intervention.

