2.1.3.2.2 Exploratory/Tertiary efficacy endpoints

2.1.3.2.2.1 Exacerbations of chronic pulmonary disease tool (EXACT)

The EXACT tool quantifies and measures exacerbations of COPD and assesses the symptomatic manifestations of these COPD exacerbations (see Appendix D). The instrument is a daily diary composed of a total of 14 items representing the following domains:

- Breathlessness (5 items),
- Cough and sputum (2 items),
- Chest symptoms (3 items),
- Difficulty bringing up sputum (1 item),
- Tired or weak (1 item),
- Sleep disturbance (1 item), and
- Scared or worried (1 item).

The EXACT total score assesses COPD exacerbations. The higher the score, the more severe are the symptoms.

The EXACT questionnaire is assessed daily from screening to Visit 16 (Week 52). Baseline EXACT score as well as the post-baseline weekly scores will be calculated as the mean within-patient score over the prior 7 days, with data present for a minimum of 4 of the 7 days. If fewer than 4 days of data are available in the 7-day window, the EXACT score cannot be calculated and will be considered as missing. For the exacerbation analysis, the baseline would be reset during

the study. Additional information related to computing scores and frequency, severity, and duration of events can be found in the user manual (6).

The Evaluating Respiratory Symptoms (E-RS) in COPD (E-RS: COPD) scale is a part of the EXACT tool. It is a derivative instrument used to measure the effect of treatment on the severity of respiratory symptoms in stable COPD. The E-RS utilizes the 11 respiratory symptom items contained in the 14-item EXACT.

The daily COPD RS-Total score is computed by taking the sum of the 11 items comprising the instrument. It has a range of 0 to 40, with higher values indicating more severe respiratory symptoms.

The same summation procedure is used to derive the three daily domain scores:

- COPD RS-Breathlessness (sum of items 7, 8, 9, 10, and 11; score range 0–17)
- COPD RS-Cough and Sputum (sum of items 2, 3, 4; score range 0–11)
- COPD RS-Chest Symptoms (sum of items 1, 5, 6; score range 0–12)

Like for EXACT, the baseline RS score as well as the post-baseline weekly domain and total scores are calculated as the mean within-patient score over the prior 7 days, with data present for a minimum of 4 of the 7 days. If fewer than 4 days of data are available in the 7-day window, the RS scores cannot be calculated and will be considered as missing.

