2.1.4 Safety endpoints

The safety analysis will be based on the reported adverse events and other safety information, such as clinical laboratory data, vital signs, ECG and physical examination.

Observation period

The observation period will be divided into 4 epochs:

- The **screening** epoch is defined as the time from the signed informed consent date up to the time prior to first administration of the IMP.

- The **treatment** epoch is defined as the time from the first administration of the IMP to the last administration of the IMP + 14 days.
- The **residual treatment** epoch is defined as the time from the last administration of the IMP +15 days to the last administration of the IMP + 98 days.

The treatment-emergent adverse event period will include both **treatment** and **residual treatment** epochs.

- The **posttreatment** epoch is defined as the period of time starting the day after the end of the treatment-emergent adverse event period up to the end of the study (defined as last protocol planned visit or the resolution/stabilization of all serious adverse events and adverse events with pre-specified monitoring).
- The on-study observation period is defined as the time from start of treatment until the end of the study (defined as last protocol planned visit or lost to follow-up or the resolution/stabilization of all serious adverse events and adverse events with pre-specified monitoring).

Safety events adjudication

Adjudication will be performed by experts independent of sponsor for the evaluation of whether deaths, cardiovascular SAEs and respiratory SAEs meet criteria for cardiovascular assessment endpoints. A confirmatory adjudication will occur for AECOPD exacerbations. Adjudicators will adjudicate these events in a consistent and unbiased manner throughout the study.

The goal of the adjudication is to ensure that all events reported by the site are judged uniformly, using pre-specified criteria by a group independent of the Sponsor. Adjudication Committee members will be blinded to treatment allocation. Adjudication Committee members' responsibilities and the process for data review are described in the AC Charter/Manual of Operation.

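### IMP compliance leaves out nearly all doses missed after a patient's last injection, so most of the misses that force discontinuation never reach the reported percentage

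*SAP*

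**What the plan says.** SAP 2.4.3.2 sets the rule for a single dose: "A given administration will be considered noncompliant if the patient did not take the planned dose of treatment as required by the protocol". A patient's percentage is the number of compliant administrations "divided by the total number of administrations that the patient was planned to take during the treatment epoch". The section then summarizes the percentages and the share of patients below 80%.

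For the epoch, 2.4.3.2 points to SAP 2.1.3.2.2.1. That is the section on the EXACT diary, and it defines no epoch. The only definition is in SAP 2.1.4, which reads: "epoch is defined as the time from the first administration of the IMP to the last administration of the IMP + 14 days". Day +14 itself belongs to this epoch, because the next one, for residual treatment, begins on day +15. The pointer for the below-80% summary is also wrong: SAP 2.4.4.5 covers exploratory efficacy endpoints.

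Protocol 6.1.1 says that IMP "is administered every 14 ± 3 days (q2w) during the 52-week treatment period". Footnote f of the schedule in Protocol 1.3.1 adds: "Last dose will be given at Week 50". Protocol 7.1.1 states: "If the patient misses more than 3 consecutive doses, the patient will be permanently discontinued from the study intervention".

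**The concern.** The denominator is anchored on the last dose taken, not on the dosing plan or on the end of assigned treatment. A patient who stops injecting remains assigned to IMP until discontinued, so the doses missed in that interval were planned, and by the SAP's own single-dose rule they are noncompliant. Restricting the denominator to the epoch removes almost all of them. The same missed dose is therefore scored differently depending only on whether a later dose follows.

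The error runs in one direction, towards better reported adherence. Patients may inject at home after one supervised injection, and the primary estimand is treatment policy. Under that estimand, mean compliance and the below-80% share help a reader judge how far a result reflects missed treatment.

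**Working it through.** The documents give no compliance figure to reproduce, so this is a direct count on the dosing schedule.

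**Inputs.** Doses are due at Weeks 0, 2, ..., 50, which is 50/2 + 1 = 26 planned doses (Protocol 1.3.1 and 6.1.1). The epoch ends on day +14 after the last administration (SAP 2.1.4). Discontinuation is triggered by the fourth consecutive miss (Protocol 7.1.1). The low-compliance threshold is 80% (SAP 2.4.3.2).

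**Where the misses fall.** After the last injection, the next four doses are due at about days +14, +28, +42 and +56. The ±3-day window can move the first to either side of the boundary, but it cannot bring the second inside. So three or all four of the triggering misses lie outside the epoch.

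**Formulas.** A patient takes the first n doses, misses the next four and is discontinued. Since n + 4 cannot exceed 26, n runs from 1 to 22.

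- SAP rule, day +14 dose counted (the literal reading): n/(n+1)
- SAP rule, day +14 dose not counted: n/n
- Planned doses counted up to the trigger: n/(n+4)

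| n taken | n/(n+1) | n/n | n/(n+4) |
|---|---|---|---|
| 1 | 50.0% | 100% | 20.0% |
| 3 | 75.0% | 100% | 42.9% |
| 4 | 80.0% | 100% | 50.0% |
| 8 | 88.9% | 100% | 66.7% |
| 9 | 90.0% | 100% | 69.2% |
| 10 | 90.9% | 100% | 71.4% |
| 15 | 93.8% | 100% | 78.9% |
| 16 | 94.1% | 100% | 80.0% |
| 22 | 95.7% | 100% | 84.6% |

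**Effect on the below-80% count.** With the misses counted, n/(n+4) is below 80% for every n up to 15. Under the literal SAP rule only n = 1 to 3 is flagged, so patients with n = 4 to 15 are overlooked. With day +14 excluded, all with n up to 15 are overlooked.

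**Misses between doses.** These stay in the denominator:

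- Every second dose taken, last at Week 48: 13/26 = 50% or 13/25 = 52%.
- One dose taken and three missed, repeated: 7/26 = 27% or 7/25 = 28%.
- Ten of 13 doses taken, with three missed in the middle, then stopping: 10/14 = 71% or 10/13 = 77%.

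The last patient took the same 10 doses as the n = 10 row, yet is reported at 71% to 77% instead of 91% to 100%.

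**Trailing misses without the trigger.** A patient who skips Weeks 46, 48 and 50 is reported at 23/24 = 96% or 23/23 = 100%, against 23/26 = 88%. The 80% threshold is not crossed.

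**The case against.** The best defence is that the SAP separates adherence while on treatment from time on treatment. The same convention of last dose + 14 days is used for exposure (SAP 2.4.3.1) and controller compliance (SAP 2.4.2.1.1). Discontinuation is tabulated by main reason (SAP 2.2), and exposure duration is summarized. The patient with 10 doses would appear there as a discontinuation with about 20 weeks of exposure. That limits the consequence, but it does not remove the inconsistency. Neither table counts missed doses: disposition gives a reason, and exposure duration ignores interruptions.

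A reader might infer that non-adherent patients in general are reported as 90% to 100% compliant, or that the worst adherence patterns are invisible. The documents support neither. Misses between doses are counted and give low percentages. Day +14 lies inside the epoch, so 90% is reached only from n = 9, n = 4 to 8 gives 80% to 89%, and patients who stop after one to three doses are still flagged.

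It is also fair that counting to the discontinuation decision makes the figure depend on how promptly that decision is recorded, and that trailing interruptions for adverse events would count as missed. The protocol does not clearly say that a decision date is captured. These objections bear on how the fix is worded.

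**Conclusion.** The concern holds for doses missed after the final administration. All of them leave the denominator except at most the one due on day +14, and these include at least three of the four misses that require discontinuation. At n = 10 the reported figure is 91% (or 100%) against 71%, a gap of 90.9 − 71.4 = 19.5 points on the literal reading.

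This rests on the epoch in SAP 2.1.4 being the one intended, since the cited section has none, and on full adherence before the four misses.

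The trial-level effect is probably small. The documents do not say how many patients would be removed under this rule. If it were 1% to 3% (an assumption), with n = 10 as typical, mean compliance would be overstated by about 0.2 to 0.6 points (0.01 × 19.5 to 0.03 × 19.5). The below-80% share could be understated by up to that same 1% to 3% of patients.

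A reader might go further and infer that efficacy conclusions are at risk. They are not: compliance is descriptive, is summarized on the safety population, and enters no efficacy model or analysis population. This is a minor correction.

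**What to change.** In SAP 2.4.3.2, define the denominator as all doses scheduled from the first dose to the earliest of:

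- Week 50;
- the recorded permanent discontinuation, or the early treatment discontinuation visit date if no decision date is captured;
- study withdrawal or death;
- the analysis cut-off.

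State that trailing missed doses before that date count as noncompliant. This also settles the treatment of the day +14 dose.

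Replace the reference to 2.1.3.2.2.1, which the new definition makes unnecessary, and correct the reference to 2.4.4.5 for the below-80% summary. Leave the safety treatment epoch in 2.1.4 unchanged.

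The cost is SAP wording, minor programming and slightly lower reported compliance. Some dependence on how promptly discontinuation is recorded remains and should be stated in a table footnote.
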